6.11.2. Analyses of Multiplicity Adjusted Objectives

A graphical approach for multiple comparisons (Bretz et al. 2011) will be used to strongly control the overall Type I error (2-sided alpha level of 0.05) for testing the treatment effect for the primary and the following multiplicity adjusted objectives: superiority of LY900014 compared with insulin lispro for (H2) 1-hour postprandial plasma glucose (PPG) excursion at the study primary endpoint, (H3) 2-hour PPG excursion at the study primary endpoint, and (H4) change from baseline to the study primary endpoint in HbA1c. Analyses will be performed for both the efficacy estimand and ITT estimand.

The graphical testing scheme for this study is displayed in [Figure 6.1](#). All the hypotheses are connected by lines with arrowheads indicating the directions of testing paths. The initial allocation of study total alpha for each hypothesis is located within the same node of the hypothesis. In this study, the study total alpha level (0.05) will be all used for the primary objective (H1) in the initial step. Then, the study total alpha level (0.05) will be allocated to other objectives according to the values of transition weights shown above the connecting lines in the figure once H1 is met. If 1 of the remaining objectives is successfully demonstrated with the given alpha level, its alpha will be allocated to the rest of objectives by the transition weights in the paths. The iterative test procedure continues until none of the remaining objectives can be demonstrated with their preserved alphas or all objectives are demonstrated successful.

An ANCOVA model with strata (pooled country, type of basal insulin, number of prandial doses at study entry, and HbA1c stratum) and treatment as fixed effects and baseline as a covariate will be used to analyze the 1-hour and 2-hour PPG excursions for both the efficacy (data collected prior to discontinuation of IP) and ITT (all data collected regardless of IP use) estimands. However, if the percentage of the patients with missing MMTT data at baseline is higher than 15%, a constrained longitudinal data analysis model (Liu et al. 2009; Lu 2010) will be used instead.

The superiority testing on change from baseline to the study primary endpoint in HbA1c will be assessed by the same analysis used for the primary objective. The analyses for the ITT and efficacy estimands are described in [Section 6.11.1](#). If the p-value is less than the alpha level allocated by the graphical approach, the superiority of LY900014 to insulin lispro will be achieved.

[figure not shown]

Figure 6.1. Testing scheme for primary and multiplicity adjusted objectives.

6.11.3. Additional Analyses of the Primary Outcome

The primary MMRM analysis model will be repeated using the PP and Completer populations as a sensitivity analysis. If the conclusion differs from that of all randomized patients, the data and analyses will be further investigated.

A secondary analysis model for the efficacy estimand will be an ANCOVA for HbA1c change from baseline to the study primary endpoint, using the model with strata (pooled country, type of basal insulin, and number of prandial doses at study entry) and treatment as fixed effects and baseline as a covariate. Missing endpoints will be imputed using the LOCF approach using post-baseline data only.

6.11.4. Sensitivity Analyses for Missing Data

A missing-not-at-random (MNAR)-based analysis will be performed for both the efficacy and ITT estimands to assess sensitivity to departures from the missing-at-random (MAR) assumption by repeatedly adjusting the imputations of missing data to provide a progressively more severe stress test (Ratitch et al. 2013). The basic idea is to impute the missing values and add a value (delta) to the imputed values of the experimental treatment group and perform an analysis for the primary endpoint on the delta-adjusted data set to see whether the conclusion of the primary analysis is overturned. If not, a larger delta is chosen and the process repeated until the primary result is overturned. If the delta required to overturn the primary result is not a plausible departure from MAR, then the primary result is robust to plausible departures from MAR. Imputation under the noninferiority null method (where delta equals the NIM) will be included as a special case of the progressive stress test.

For the ITT estimand, the reference group will be as described for the **CC1** primary analysis, and ANCOVA on the change from baseline to Week 26 in HbA1c will be used.

For the efficacy estimand, the reference group will be the insulin lispro treatment group. Imputation will be for all longitudinal visits.

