10.1. Sample Size Determination

Approximately 670 patients will be randomized in order that 568 patients complete the study through the primary endpoint at Week 26.

The primary objective of this study is to test the hypothesis that LY900014 is noninferior to insulin lispro on glycemic control as measured by change from baseline to Week 26 in HbA1c in patients with T2D when administered in a double-blind manner as prandial insulin in combination with basal insulin glargine or insulin degludec and OAM.

Patients will be randomized in a 1:1 ratio to LY900014 and insulin lispro, both dosed 0 to 2 minutes before meals. Assuming a noninferiority margin (NIM) of 0.4%, no true difference between treatment groups, and an SD of 1.1%, 568 completers (284 in each group) will provide greater than 99% power to show noninferiority between LY900014 and insulin lispro using the upper limit of a 2-sided 95% confidence interval (CI) (LY900014 – insulin lispro). CCI

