5.2. Determination of Sample Size

Assuming a noninferiority margin (NIM) of 0.4%, no true difference between treatment arms, and a standard deviation (SD) of 1.1%, 568 completers (284 in each treatment group) will provide at least 99% power to show noninferiority between LY900014 and insulin lispro in change from baseline to 26 weeks in hemoglobin A1c (HbA1c) using the upper limit of a 2-sided 95% confidence interval (CI) (LY900014 – insulin lispro). **CCI**

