5.3. Method of Assignment to Treatment

Patients who meet all criteria for enrollment will be randomized to double-blind treatment at Visit 8. Assignment to treatment groups will be determined by a computer-generated random sequence using an interactive web-response system (IWRS). Patients will be randomized to 1 of the 2 treatment groups in 1:1 ratio (double-blind LY900014 administered at meal time, double-blind insulin lispro administered at meal time). Stratification will be by country, HbA1c stratum ($\leq 8.0\%$, $> 8.0\%$ at Visit 7), and type of basal insulin during the lead-in period (glargine U-100 or degludec [U-100 or U-200]), and number of prandial doses at study entry (< 3 , ≥ 3).

Abbreviations: T = telephone visit; wk = week.

- a At Visit 2, patients treated with insulin aspart, insulin glulisine, regular insulin, or premixed insulin will be transferred to insulin lispro. At Visit 2, patients treated with a basal insulin regimen other than insulin glargine U-100 or insulin degludec will be transferred to an allowed study basal regimen of insulin glargine U-100 once or twice daily or insulin degludec U-100 or U-200 once daily. At Visit 8, patients will be randomized to either insulin lispro or LY900014 and continue their basal insulin regimen.
- b Titrate basal insulin.
- c Titrate prandial insulin (insulin lispro or LY900014).
- d Patients will discontinue study insulins at Week 26.
- e Eligible patients will have visits at approximately 3-month intervals for up to 26 weeks after Visit 801 for follow-up of insulin lispro antibody levels.

Figure 5.1. Illustration of study design.

6. A Priori Statistical Methods

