CCI [REDACTED], the primary efficacy comparison will be based on the contrast between LY900014 and insulin lispro at Week 26 (Visit 18) from the MMRM analysis of change from baseline in HbA1c including data collected from all randomized patients prior to permanent discontinuation of IP through Week 26 (efficacy estimand). The model for the analysis of the primary efficacy endpoint of change from baseline in HbA1c will include the fixed class effects of treatment, strata (pooled country, type of basal insulin, and number of prandial doses at study entry), visit, and treatment-by-visit interaction, as well as the continuous, fixed covariates of baseline value. An unstructured covariance structure will be used to model the within-patient errors. Significance tests will be based on LS means and Type III tests. If this analysis fails to converge, the following covariance structures will be tested in order:

- Toeplitz with heterogeneity
- autoregressive with heterogeneity
- compound symmetry with heterogeneous variances
- Toeplitz
- autoregressive
- compound symmetry without heterogeneous variances

The first covariance structure that converges will be used. The Kenward-Roger approximation will be used to estimate denominator degrees of freedom.

For both primary analysis approaches, LY900014 will be declared noninferior to insulin lispro if the upper limit of the 2-sided 95% CI for the LS mean difference in the change from baseline in HbA1c for LY900014 minus insulin lispro is below +0.4%. In addition, the 95% CI for the treatment difference will be compared to an alternative NIM of +0.3%. Both estimands will be tested at the full significance level of 0.05.

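### For the efficacy estimand the delta stress test starts from lispro-based imputation but is read as a departure from MAR; the two differ by a fraction of the observed treatment difference

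*SAP*

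**What the plan says.** SAP 6.11.4 plans a tipping-point analysis for both estimands. Missing HbA1c values are imputed, a delta is added to the imputed values in the LY900014 arm only, and delta is raised until the primary conclusion fails. The rule for reading the result begins "If the delta required to overturn the primary result is not a plausible departure from MAR"; in that case the primary result counts as robust. Setting delta equal to the noninferiority margin is included as a special case.

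The section then names a reference for each estimand. The ITT estimand uses the reference of its primary analysis, which SAP 6.11.1 defines as patients of the same treatment group who stopped study drug but completed the study. For the other estimand: "For the efficacy estimand, the reference group will be the insulin lispro treatment group". Imputation covers all longitudinal visits. Protocol 10.3.3.1.1 says the same.

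The analysis being stressed is in SAP 6.11.1: an MMRM on data before permanent discontinuation of study drug, with treatment and treatment-by-visit terms. Nothing is imputed from the other arm.

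**The concern.** A tipping delta means something only relative to its starting point. The MMRM treats LY900014 dropouts as MAR within their own arm, so a departure from MAR should be counted from there. If LY900014 dropouts are first given lispro-like values, delta = 0 already differs from MAR whenever the arms differ. Neither document converts delta back to a distance from MAR.

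The direction matters for noninferiority. If LY900014 is numerically worse, the lispro base improves its imputed values before any stress is applied. Part of the reported delta then only restores the MAR position. This happens where the stress test is most needed, with the upper confidence limit close to 0.4%. What is at stake is the robustness statement for the efficacy estimand.

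**Working it through.** **Inputs from the documents.** SAP 5.2: "Assuming a noninferiority margin (NIM) of 0.4%, no true difference between treatment arms, and a standard deviation (SD) of 1.1" (HbA1c percentage points), and "568 completers (284 in each treatment group) will provide at least 99% power to show noninferiority", judged "using the upper limit of a 2-sided 95% confidence interval (CI) (LY900014 – insulin lispro". SAP 5.3 gives 1:1 allocation. Protocol 10.1: "Approximately 670 patients will be randomized in order that 568 patients complete the study through the primary endpoint at Week 26". SAP Table 6.2 gives post-baseline HbA1c at Visits 11, 13, 15 and 18 (Weeks 4, 8, 12 and 26) and requires at least one post-baseline value on study drug.

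**Assumptions not in the documents.** The missing share f is set to planned non-completion, 102/670 = 15.2% (5% and 10% also shown). The observed difference d is varied. SE is held fixed as delta grows. Delta is added at Week 26.

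**The plan's own figure.** SE = 1.1 × √(2/284) = 0.0923. Power = Φ(0.4/0.0923 − 1.96) = Φ(2.37) = 99.1%, which agrees with the stated 99%. The documents give no tipping delta to reproduce.

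**Formulas.** Let h = 0.4 − 1.96 × 0.0923 = 0.219, the largest d that still shows noninferiority.
- Within-arm MAR base: the difference is d + f × delta, so the tipping delta is (h − d)/f.
- Lispro base, earlier visits not used: the difference is (1 − f)d + f × delta, so the tipping delta is (h − (1 − f)d)/f = (h − d)/f + d.

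The gap is exactly d, whatever f is.

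| d | MAR base | Lispro base (maximum gap) |
|---|---|---|
| −0.10 | 2.10 | 2.00 |
| 0 | 1.44 | 1.44 |
| +0.05 | 1.11 | 1.16 |
| +0.10 | 0.78 | 0.88 |
| +0.15 | 0.45 | 0.60 |
| +0.20 | 0.13 | 0.33 |

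For d = 0.10: (0.219 − 0.10)/0.152 = 0.78, and 0.78 + 0.10 = 0.88.

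**Sensitivity of the d = 0.20 row.** With f = 10% it is 0.19 against 0.39; with f = 5%, 0.38 against 0.58. With f = 15.2% and 335 per arm (SE 1.1 × √(2/335) = 0.085, h = 0.233), it is 0.22 against 0.42.

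**If imputation conditions on earlier visits.** Part of the arm difference is carried by the patient's own data. With equal correlation ρ between visits, k visits observed and a constant d, the Week 26 shift is d × [1 − kρ/(1 + (k − 1)ρ)].
- ρ = 0.5: 0.50d, 0.33d and 0.25d for k = 1, 2, 3; mean 0.36d.
- ρ = 0.7: 0.30d, 0.18d and 0.13d; mean 0.20d.
- ρ = 0.85: 0.15d, 0.08d and 0.06d; mean about 0.10d.

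If the difference instead grows in proportion to time (4/26, 8/26 and 12/26 of d at the early visits), k is replaced by the sum of those fractions. With ρ = 0.5 the shifts are 0.92d, 0.85d and 0.77d, mean 0.85d. Roughly 0.1d to 0.9d is therefore a fair range among patients with at least one post-baseline value.

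**Simulation check.** With 335 per arm, SD 1.1%, a constant d, sequential regression imputation and dropout spread evenly over the four visits (including before Week 4), the gap at d = 0.20 was 0.10 (ρ = 0.5) and 0.08 (ρ = 0.7). The formula with k = 0 included gives (1 + 0.50 + 0.33 + 0.25)/4 × 0.20 = 0.10 and (1 + 0.30 + 0.18 + 0.13)/4 × 0.20 = 0.08. At d = 0.10 the simulated gap was about 0.06, with noise of about 0.02.

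**At delta = 0.4.** The MAR base fails once d exceeds 0.219 − 0.152 × 0.4 = 0.158; the lispro base fails once d exceeds 0.158/0.848 = 0.187. With no use of earlier visits, the two disagree only for d of about 0.16 to 0.19.

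**The case against.** **The reading is inferred.** SAP 6.11.4 does not redefine the reference group for this estimand. It also leaves open whether imputation uses earlier visits and whether delta enters at every visit or only at Week 26. This is fair, and the size depends on those choices. Still, SAP 6.11.1 and the parallel ITT sentence both use the word for the patients whose data feed the imputation, so this is the natural reading.

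**A lispro base is legitimate.** Lispro-based imputation plus delta is a recognised missing-not-at-random analysis, and lispro plus 0.4% is exactly the noninferiority null, which the section wants as a special case. This stands. A reader might infer that naming lispro is simply a mistake; the documents do not support that. The mismatch is that one base is specified for two readings, and they coincide only when the arms are equal.

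**It is small and unlikely to bite.** At the planning assumption of no true difference there is no systematic offset. If the true difference is 0 and SE is 0.0923, an observed d of 0.15 or more has probability of about 5%, and 0.20 or more about 1.5%. The chance that d lies between 0.15 and the noninferiority limit is about 4%, rising to about 20% if the true difference is +0.1. This stands as a limit on importance.

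**Other checks exist.** The MMRM is repeated in the per-protocol and completer sets, an LOCF ANCOVA is added, and the ITT stress test uses a same-arm reference. None of these is a within-arm MAR tipping analysis for the efficacy estimand.

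**Conclusion.** The concern holds as a mismatch between how delta is generated and how it is read. The reported tipping delta differs from the distance from MAR by at most d, and by roughly 0.1d to 0.9d if imputation uses earlier visits and patients without a post-baseline value are excluded. Since noninferiority requires d below about 0.22, the overstatement cannot exceed about 0.22 points. It is material only for a narrow noninferiority result with LY900014 worse by about 0.15 or more. At d = 0 there is none, and when LY900014 is better the lispro base is conservative.

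Two stronger inferences are not supported. A reader might think the noninferiority decision itself is biased; it rests on the confidence intervals in SAP 6.11.1, which this analysis does not touch. A reader might also want one percentage for the overstatement. None is stable: without use of earlier visits, the ratio runs from 1.13 at d = 0.10 to 2.6 at d = 0.20 with f = 15.2%, and at d = 0.20 it falls to 1.5 with f = 5%.

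The figures rest on SD 1.1%, 284 per arm, the assumed missing share and the inferred meaning of the reference group.

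**What to change.** In SAP 6.11.4, for the efficacy estimand, impute both arms under MAR within arm, add delta to the LY900014 imputations, and report that tipping delta as the departure from MAR. Keep lispro-referenced imputation plus 0.4% as a separately labelled noninferiority-null analysis. State whether imputation conditions on earlier visits and at which visits delta is added.

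The cost is one additional imputation run and a few sentences of SAP text. No new data are needed, and the primary analysis is unchanged.

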6.11.5. Other Secondary Efficacy Analyses

The analyses described in Section 6.11.5 to Section 6.11.7 will include data collected from all randomized patients prior to permanent discontinuation of IP. The longitudinal observations of actual and change from baseline in HbA1c up to Week 26 will be analyzed using the same MMRM model as for the analysis of the primary outcome. For the following secondary efficacy endpoints, an MMRM model similar to that for the primary outcome with an additional term of HbA1c stratum ($\leq 8\%$, $> 8\%$) will be used:

- actual and change from baseline 1,5-AG values
- actual and change from baseline 10-point SMBG values (fasting, 1 hour post morning meal, 2 hours post morning meal, pre midday meal, 1 hour post midday meal, 2 hours post midday meal, pre evening meal, 1 hour post evening meal, 2 hours post evening meal, and bedtime)
- actual and change from baseline in total, basal, and prandial insulin doses and prandial/total insulin dose ratios

Three 10-point SMBG profiles are expected to be collected during the 2 weeks prior to specified visits. Valid SMBG profiles will be used for analysis, defined as having non-missing values at ≥ 6 time points among the 10 pre-specified time points and being collected during 2 weeks prior to a given visit. For each time point, the average of the corresponding SMBG values from the valid SMBG profiles will be used for analysis. The excursion of SMBG for each meal category (that is, morning meal, midday meal, and evening meal) calculated using the average values at the corresponding time points will be used for analysis.

The following endpoints, collected from the MMTT, will be analyzed using the ANCOVA model with strata (pooled country, type of basal insulin, number of prandial doses at study entry, and HbA1c stratum) and treatment as fixed effects and baseline as a covariate:

- actual and change from baseline in fasting glucose (average of measurements at time -15 and 0), and PPG at 15, 30, 60, 120, 180, and 240 minutes after the meal
- PPG excursions at time 15, 30, 180, and 240 minutes after the meal (PPG minus fasting glucose)

Sensitivity analysis for PPG excursions may be performed to exclude patients whose PPG excursion could be affected by factors including MMTT consumption amount (for example, partial MMTT was consumed) and correction bolus insulin usage.

Treatment comparisons for the proportion of patients with HbA1c $< 7.0\%$ and $\leq 6.5\%$ will be analyzed using a longitudinal logistic regression with repeated measurements conducted by a generalized linear mixed model including independent variables of treatment, baseline HbA1c value, visit, baseline HbA1c-by-visit interaction, and treatment-by-visit interaction. An unstructured covariance structure will be used. As a sensitivity analysis, the proportion of patients with HbA1c $< 7.0\%$ and $\leq 6.5\%$ at Week 26 (Visit 18), imputed using LOCF, will be compared using a logistic regression model with terms for treatment and baseline HbA1c value.

6.11.6. Secondary Health Outcomes Analyses

For the Insulin Treatment Satisfaction Questionnaire (ITSQ), the change from baseline to LOCF endpoint while on treatment in each domain transformed score (inconvenience, lifestyle, hypoglycemic control, glycemic control, delivery system) and overall transformed score will be analyzed using the ANCOVA model with strata (pooled country, type of basal insulin, number of prandial doses at study entry, and HbA1c stratum), and treatment as fixed effects and baseline as a covariate.

6.11.7. Analyses of Exploratory Objectives

Summary statistics, including number of patients and proportion of categorical outcomes (5 levels) for the 5 dimensions (mobility, self-care, usual activity, pain/discomfort, and anxiety/depression) of the European Quality of Life – 5 Dimensions 5 Level (EQ-5D-5L) will be provided by visit and by treatment. The change from baseline to LOCF endpoint (Week 26, Visit 18) in the EQ-5D-5L United Kingdom (UK) population-based health state index score and EuroQol visual analog scale (EQ-VAS) score will be analyzed using the ANCOVA model with terms same as those for ITSQ analysis described in Section 6.11.6.

For the Work Productivity and Activity Impairment Questionnaire General Health (WPAI-GH), the change from baseline to LOCF endpoint in each score (absenteeism, presenteeism, work productivity loss, and activity impairment) will be analyzed using the ANCOVA model similar to ITSQ.

The proportions of patients with HbA1c <8%, ≤8%, <9% and ≤9% at Week 26 will be summarized by treatment.

Within-day and between-day glycemic variability measured by the SD and the coefficient of variation (CV) of 10-point SMBG profiles will also be analyzed by MMRM model specified in Section 6.11.5. At a given visit, the CV and SD on each day with a valid SMBG profile will be calculated using all the glucose values within that day, then the average values of these CVs and SDs will be used as the within-day CV and SD at that visit in analysis. At a given visit, the CV and SD at each of the 10 pre-specified SMBG time points will be calculated using the corresponding glucose values of the valid SMBG profiles, then the average values of these CVs and SDs will be used as the between-day CV and SD at that visit in analysis. Table 6.4 lists additional variables for potential exploratory analyses.

Table 6.4 Additional Exploratory Efficacy Variables

Variable Description	Derivation	Statistical Method
Incremental areas under the serum glucose concentration-time curve from 0 to 30 minutes, 0 to 1 hour, 0 to 2 hours, 0 to 3 hours, and 0 to 4 hours after the meal in MMTT.	iAUC+: the total area under the serum glucose curve but above the glucose level at time 0 when the meal starts for the MMTT within the specific time frame. The area will be calculated by trapezoids rule.	ANCOVA
Area under/above the serum glucose concentration time curve from 0 to 30 minutes, 0 to 1 hour, 0 to 2 hours, 0 to 3 hours, and 0 to 4 hours after the meal in MMTT.	
 AUC: Total area under the serum glucose curve calculated by trapezoids area within the specific time frame AUC_{>180}: Total area under the serum glucose curve but above the 180 mg/dL level within the specific time frame AOC_{≤70}: Total area above the serum glucose curve but below the 70 mg/dL level within the specific time frame. 	ANCOVA
Glucose variability during MMTT	
 The CV of all serum glucose values collected during the MMTT The SD of all serum glucose values collected during the MMTT. 	ANCOVA
1-hour and 2-hour PPG excursions by 10-point SMBG profile and daily average of the 10-point SMBG profile	
 The difference in means between 1-hour PPG and fasting PG at the same visit The difference in means between 2-hour PPG and fasting PG at the same visit. The average of daily mean of the 10-point SMBG profile at the same visit 	MMRM
Incidence of HbA1c ≤6.5% and <7.0% without severe hypoglycemia	
 Binary indicator with 1 indicating HbA1c ≤6.5% at Week 26 and no severe hypoglycemia during 0-26 weeks of treatment Binary indicator with 1 indicating HbA1c <7% at Week 26 and no severe hypoglycemia during 0-26 weeks of treatment. 	Logistic regression

Abbreviations: ANCOVA = analysis of covariance; AOC = area over the curve; AUC = area under the curve; CV = coefficient of variation; iAUC = incremental area under the curve; HbA1c = hemoglobin A1c; MMTT = mixed-meal tolerance test; MMRM = mixed-effect model repeated measures; PPG = postprandial glucose; SD = standard deviation; SMBG = self-monitored blood glucose.

